7.2 Participant Discontinuation/Withdrawal from the Study

A patient may withdraw from the study at any time at his/her own request or may be withdrawn at any time at the discretion of the Investigator for safety, behavioral or administrative reasons. The patient will be definitively discontinued from both the study drug and from the study at that time.

The primary reason for a patient withdrawing prematurely should be recorded in the patient's source records and on the eCRF. In the absence of a medical contraindication or significant protocol violation, every effort will be made by the Investigator to keep the patient in the study. Patients who discontinue study drug because of an AE but agree to participate with any follow-up assessments will undergo the EOT/ED Visit and will be requested to return for the Follow-up Visits. The Investigator must contact the Medical Monitor promptly when deciding if a patient should be withdrawn or if the patient elects to stop the study.

Patients withdrawn from this study cannot re-enroll. Patients who discontinue for a non-safety related reason may be replaced if the patient is withdrawn during Cycle 1 in Part 1. Withdrawal of consent must be ascertained and documented by the Principal Investigator who must consult with the Medical Monitor and document the withdrawal of consent in the eCRF and in the medical records. Patients will be asked about the reason(s) for withdrawal and the presence of any AEs. Should the patient agree to be followed for safety information, this should be documented in the medical records.

Patients experiencing adverse reactions should be followed until the AE has resolved, stabilized or is no longer deemed clinically significant, as judged by the Investigator. Appropriate supportive and/or definitive therapy will be administered as required.

If the patient withdraws consent for disclosure of future information, the Sponsor may retain and continue to use any data collected before such a withdrawal of consent.

If a patient withdraws from the study, he or she may request destruction of any samples taken and not tested and the Investigator must document this in the site study records.

At the time of discontinuing from the study, if possible, an early discontinuation visit should be conducted, as shown in the SoA. Refer to the SoA (Table 1-1 [Parts 1 and 2]) for data to be collected at the time of study discontinuation and follow-up and for any further evaluations that need to be completed.

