The expected study duration for each patient from initial administration of NOX66 until the last study visit is determined by the number of treatment cycles each patient receives plus the follow-up period, which is from the last dose of NOX66 until death or the patient is lost to follow-up.

The study will finish when the last patient enrolled in Part 2 completes 6 months of treatment and all patients receiving study drug at that time will be switched to the NOX66 compassionate access program. Those patients on the compassionate access program will continue to receive NOX66 treatment until disease progression or unacceptable toxicity. These patients will be followed until death, or the patient is lost to follow-up.

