- * The procedures detailed at Cycle 5 Day 1 will be performed for all subsequent on-site visits (unless otherwise specified). Patients will continue NOX66 administration in each cycle from Day 1 until Day 7 followed by a 7-day rest period (Days 8 to 14).

It is important that PK sampling occurs as close as possible to the scheduled time. In order to achieve this, other assessments scheduled at the same time may be initiated prior to the timepoint. The order of assessments (as applicable to study visit) that should occur before dosing is: 1) PRO questionnaires, 2) vital signs, 3) ECG, 4) PK sampling, 5) dose administration. Blood sampling for safety laboratory assessments will be done prior to dosing. The order of assessments (as applicable to the study visit) that should occur after dosing is: 1) vital signs, 2) ECG, 3) PK sampling. All other procedures can be completed (as applicable to study visit) after the PK sample has been collected. It is critical that the patients record the time of dose in their Patient Study Drug Administration Diary for the PK assessment and the site record the time of blood sampling.

- ^{a.} End of Treatment Visit (EOT) occurs 7 to 10 days after the last dose of study drug. Assessments completed within 7 days prior to the last dose of study drug do not need to be repeated. If a patient discontinues from the study early (Early Discontinuation [ED]), they will have an ED Visit within 7 to 10 days after the last dose of study drug.
- ^{b.} For patients who permanently discontinue study drug for any reason other than confirmed disease progression, tumor imaging and disease response assessments will continue to be performed every 12 weeks (± 7 days) for up to 12 months after the last dose of the study drug until disease progression, withdrawal of consent, initiation of new anticancer therapy, the patient is lost to follow-up or death, whichever comes first.
 - If a patient meets disease progression during the follow-up period according to RECIST v1.1 criteria, a tumor imaging and disease response assessment is not required.
 - If a patient permanently meets clinical disease progression during the follow-up period, a tumor imaging and disease response assessment does not need to be repeated if completed ≤ 28 days after the date of clinical disease progression.
 - Patients who have met disease progression will be contacted every 3 months for survival follow-up.

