At a minimum, imaging of the chest, abdomen and pelvis should be performed using consistent imaging modality (computerized tomography [CT] or magnetic resonance imaging [MRI]). As far as possible, the same imaging method should be used for the patient throughout the study.

- W. Questionnaire to be completed at Screening, Day 1 of Cycle 3, Day 1 of Cycle 5 followed by every 4 cycles thereafter (e.g., Cycle 9, Cycle 13 etc.) and at the EOT/ED Visit. Questionnaire to be completed prior to performing any other study visit assessments on the day of the visit.
- x Questionnaire to be completed on Day 2 of Cycle 1, Day 1 of Cycle 3 and at the EOT/ED Visit. Questionnaire to be completed prior to performing any other study visit assessments on the day of the visit (excluding predose clinical laboratory assessment for Cycle 1 Day 1 which may be completed within 3 days prior to Day 1).
- ^{y.} May be an in-person visit or a phone call. Only applicable to patients who have met disease progression.
- ^{z.} Pharmacokinetic samples are to be obtained on Days 1, 2, 6, 14 and 15 of Cycle 1, and Days 1 and 8 of Cycles 2 and 3. See PK sampling schedule in Table 1-3. For Part 2, PK sampling will only be performed for the first 10 patients enrolled for each tumor group (mCRPC, breast cancer or non-small-cell lung cancer).
- aa. Pharmacodynamic blood samples to be collected at Screening or Cycle 1 on Days 1 and 15, prior to dosing on Day 1 of Cycle 3 (during the rest period after patients have completed 7-days of NOX66 treatment in Cycle 2, or predose on Day 1 of Cycle 3) and at the EOT/ED Visit. See PD sampling schedule in Table 1-4.
- ^{bb.} Patients will be asked whether they are willing to provide both archival and fresh tissue biopsy samples OR only fresh tissue biopsy if they do not have archival tissue samples. Available archival tissue samples will only be requested if a fresh tissue biopsy is collected after Cycle 3. Provision of a fresh biopsy sample and/or an archival tissue sample is optional. See Table 1-5.

- ^{cc.} On days when study drug and EBRT are to be administered, it is advisable that NOX66 is given at least 1 hour prior to EBRT. Twice daily of NOX66 dosing should occur at least 10 hours apart. Where 2 suppositories are administered per dosing, each suppository will be administered at least 5 minutes apart.

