Patients in both study parts will be followed up by phone for AEs/SAEs for 30 days after the last dose of study drug or until resolution or stabilization of ongoing AEs/SAEs deemed at least possibly related to the study drug, whichever is longer. All patients (including patients who discontinued the study early for reasons other than disease progression) will be followed up approximately every 12 weeks (\pm 2 weeks) after completion of the treatment period for disease progression up to 12 months, and for safety until death, or the patient is lost to follow-up. Patients who discontinued the study early for reasons other than disease progression will attend the clinical unit for the follow-up visits. Patients will receive the study drug until disease progression, unacceptable toxicity, withdrawal of consent, initiation of new anticancer therapy, withdrawal of the patient by the Investigator or termination of the study by the Sponsor. Tumor imaging and disease response assessments will be performed for up to 12 months after the last dose of study drug until disease progression, withdrawal of consent, initiation of new anticancer therapy, the patient is lost to follow-up or death, whichever comes first.

The study will include 4 dose cohorts (Part 1) and 2 treatment arms (Part 2):

- Part 1: Eligible patients with any solid tumor will be enrolled in one of 4 dose cohorts:
 - Dose Cohort 1: 800 mg NOX66 (Days 1 to 14 [Cycle 1]) + EBRT (Days 2 to 11 of Cycle 1, depending on the number of fractions to be administered). From Cycle 2 onwards, 800 mg NOX66 will be administered on Days 1 to 7.
 - Dose Cohort 2: 1200 mg NOX66 (Days 1 to 14 [Cycle 1]) + EBRT (Days 2 to 11 of Cycle 1, depending on number of fractions to be administered). From Cycle 2 onwards, 1200 mg NOX66 will be administered on Days 1 to 7.
 - Dose Cohort 3: 1600 mg NOX66 (Days 1 to 14 [Cycle 1]) + EBRT (Days 2 to 11 of Cycle 1, depending on number of fractions to be administered). From Cycle 2 onwards, 1600 mg NOX66 will be administered on Days 1 to 7.
 - Dose Cohort 4: 2400 mg NOX66 (Days 1 to 14 [Cycle 1]) + EBRT (Days 2 to 11 of Cycle 1, depending on number of fractions to be administered). From Cycle 2 onwards, 2400 mg NOX66 will be administered on Days 1 to 7.
- Part 2: Eligible patients will be enrolled in 1 of 2 treatment arms:

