4.4 End of Study Definition

Once a patient completes or discontinues study drug, he/she will be followed up every 12 weeks $(\pm 2 \text{ weeks})$ after the last dose of study drug for disease progression up to 12 months, and for safety until death or the patient is lost to follow-up.

For the entire study, study completion is defined as the last visit of the last patient for any protocol related activity (last patient, last visit), including telephone contact. For individual patients, study completion is defined as the time of the patient's last data collection.

The study will finish when the last patient enrolled in Part 2 completed 6 months of treatment; all patients receiving study drug at that time will be switched to the NOX66 compassionate access program. Those patients on the compassionate access program will continue to receive NOX66 treatment until disease progression or unacceptable toxicity. These patients will be followed until death, or the patient is lost to follow-up.

5 Study Population

The study population will consist of patients with mCRPC, BC, NSCLC or other solid tumors who have failed at least one line of prior treatment and for whom, according to the Investigator, are eligible for low-dose EBRT for at least one symptomatic or minimally symptomatic lesion (for the prevention of symptoms).

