7.1 Discontinuation of Study Drug

7.1.1 Safety Stopping Criteria:

It may be necessary for a patient to permanently discontinue (definitive discontinuation) study drug. If study drug is definitively discontinued, the patient will remain in the study to be evaluated for clinical observation and safety monitoring. See the SoA (Table 1-1 [Parts 1 and 2]) for data to be collected at the time of discontinuation of study drug and follow-up and for any further evaluations that need to be completed.

Patients may be discontinued from study drug in the following situations:

- Patient decision. The patient free to discontinue study drug at any time, without prejudice to further treatment.
- Any AE that in the opinion of the Investigator or Sponsor contraindicates dosing or meets the criteria for discontinuation.
- Recurrence of the same Grade 3 AE, even if recurrence is at a lower dose of study drug, with the exemption of localized skin reactions associated with drug administration which responds to topical corticosteroids.
- Unacceptable toxicity.
- Severe noncompliance with the protocol.
- Disease progression or unacceptable toxicity.
- Patient started alternative anticancer therapy including another investigational agent.
- Patient is lost to follow-up.

For patients with mCRPC, study drug will not be stopped due to rises in PSA alone. The Prostate Cancer Working Group 3 (PCWG-3) emphasized the importance of keeping patients on the study until radiographic or symptomatic progression, which better reflects the clinical course.

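### Survival-status contact is limited to progressed patients, and Section 7.2 takes investigator-withdrawn patients off study, so OS can be censored informatively despite the promise to follow everyone until death

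*Combined protocol and SAP*

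**What the plan says.** Three sets of statements in the current text bear on who is followed for survival.

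- **All patients, until death or loss.** Section 4.1: "All patients (including patients who discontinued the study early for reasons other than disease progression) will be followed up approximately every 12 weeks". Section 4.4 applies this to anyone who completes or stops study drug: "for disease progression up to 12 months, and for safety until death or the patient is lost to follow-up". The synopsis defines each patient's follow-up period in the same way: "which is from the last dose of NOX66 until death or the patient is lost to follow-up". Section 7.1.1 adds: "If study drug is definitively discontinued, the patient will remain in the study to be evaluated for clinical observation and safety monitoring".
- **Progressed patients only.** In Table 1-1, footnote y to the survival-status row reads: "May be an in-person visit or a phone call. Only applicable to patients who have met disease progression". Footnote b says: "Patients who have met disease progression will be contacted every 3 months for survival follow-up". No footnote sets a survival contact for a patient who has not progressed.
- **Off study at withdrawal.** Section 7.2 covers a patient who withdraws, or who is "withdrawn at any time at the discretion of the Investigator for safety, behavioral or administrative reasons", and states: "The patient will be definitively discontinued from both the study drug and from the study at that time". It goes on to mention follow-up visits for patients who stop drug because of an AE and agree to them, and safety follow-up if the patient agrees. It does not mention survival.

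Section 8.1.9 defines OS from first dose to death from any cause and has one censoring rule, the date last known alive. Section 9.4.7.2 estimates OS by Kaplan-Meier and reports medians with 95% CIs.

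**The concern.** A site cannot satisfy all of these statements at once. Section 8 calls adherence to the Schedule of Activities essential, and a site that works from that schedule and from Section 7.2 will not deliver the follow-up until death that Section 4.1 describes.

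Kaplan-Meier assumes that patients censored at a given time have the same outlook as those still followed. Safety is one of the listed reasons for investigator withdrawal, so a link with prognosis is plausible in that group. If withdrawn patients die sooner than the others and their deaths are not recorded, OS is overstated. There is no control arm in which a similar bias could cancel. Vital status that is not collected during the study may not be recoverable at analysis.

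**Working it through.** The plan gives no OS figure, event count or dropout rate to reproduce. The check is a comparison of the texts, followed by an illustration of size.

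**1. Who has a survival contact under each text**

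| Patient | Synopsis, 4.1, 4.4 | Table 1-1 footnotes b, y | Section 7.2 |
|---|---|---|---|
| Progressed | Until death or loss | Every 3 months | Not addressed |
| Drug stopped, not progressed, within 12 months | Until death or loss | Clinic visits and imaging, so vital status is known | AE stoppers who agree return for visits |
| Not progressed, new anticancer therapy started | Until death or loss | Imaging and PSA end; no survival contact | Not addressed |
| Not progressed, past the 12-month window | Until death or loss | No survival contact | Not addressed |
| Withdrawn by the Investigator | Until death or loss (early discontinuers are included) | Survival contact only if progressed | Off study; safety follow-up by agreement |

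The exposed groups are the last three rows.

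**2. Bound that needs no assumption about prognosis**

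Each patient lost before a landmark may be alive or dead at it, so the landmark estimate has a range of (number lost)/n.

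- Arm 1, n = 40: 1/40 = 2.5 points per patient; 4 lost gives 4/40 = 10 points.
- Arm 2, n = 24 (the lower end of 24 to 30): 1/24 = 4.2 points per patient; 4 lost gives 4/24 = 16.7 points.

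The number lost is an assumption.

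**3. Illustration of the bias for withdrawn patients**

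Assumed inputs, none from the documents:

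- exponential survival with median 12 months, so λ = ln 2 / 12 per month
- a share w marked for withdrawal at a time uniform over months 0 to 6, and censored there if still alive
- a death hazard after withdrawal of k times λ

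Censoring at withdrawal leaves only hazard λ in view, so Kaplan-Meier estimates S(12) = 0.500 whatever w and k are. With full follow-up,

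S(12) = (1 − w) × 0.5 + w × A(k), where A(k) = 0.5^k × [exp(6(k−1)λ) − 1] / [6(k−1)λ] and 6λ = 0.3466.

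- k = 2: A = 0.25 × (1.4142 − 1)/0.3466 = 0.299
- k = 3: A = 0.125 × (2 − 1)/0.6931 = 0.180

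Overstatement = w × (0.5 − A):

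| w | k = 1 | k = 2 | k = 3 |
|---|---|---|---|
| 5% | 0 | 0.05 × 0.201 = 1.0 points | 0.05 × 0.320 = 1.6 points |
| 10% | 0 | 0.10 × 0.201 = 2.0 points | 0.10 × 0.320 = 3.2 points |

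A simulation of 400,000 patients agrees for w = 10%, k = 2: 50.0% with censoring against 47.9% with full follow-up, and a median of 12.0 against 11.3 months. For comparison, the binomial SE of a 50% rate with n = 40 is √(0.5 × 0.5/40) = 7.9 points.

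**4. Non-progressed patients**

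No size is given for this group. The direction is also open: a patient still free of progression 12 months after the last dose may well have a better outlook than average, and censoring such patients would then pull OS down.

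**The case against.** **Stopping drug is not leaving the study.** Section 7.1.1 keeps patients in the study after AEs, unacceptable toxicity, severe noncompliance, progression or alternative therapy. Section 7.2 also asks for every effort to keep patients in the study, and it points to the Schedule of Activities for follow-up after discontinuation. This stands and narrows the exposed group. A reader might infer that Section 7.2 forbids all contact after an investigator withdrawal. It does not say so, and it allows safety follow-up by agreement. But that agreement does not name survival, and the schedule it points to limits survival status to progressors.

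**The schedule still has contacts.** The 12-weekly follow-up column marks phone call, AE and SRE/SSE rows without footnote y, and non-progressed early discontinuers attend the clinic. This too stands: their gap opens only at new therapy or after 12 months. The marks do not close it. Footnote e ties the phone calls to on-site visits and to the 30-day call, and footnote t ends AE collection 30 days after the last dose or when related events settle.

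**PFS.** A reader might infer that PFS is overstated in the same way. The documents do not support that: Section 8.1.8 lists early discontinuation among the PFS events, so a withdrawn patient is not simply censored.

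**Size and weight.** Every input to the illustration is assumed. The shifts are well below the 7.9-point SE, and 12-month OS is not a named estimate in Section 9.4.7.2. OS is one of many secondary endpoints, and Section 9.1 rules out hypothesis tests. All of this is correct and limits the weight of the point. It does not remove the contradiction.

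**Conclusion.** The point holds as a conflict over who is followed for survival, with a possible informative-censoring bias in OS. It is confined to investigator-withdrawn patients, and to non-progressed patients after new anticancer therapy or after the 12-month window. The documents do not allow the bias to be sized. Under the assumptions shown (median 12 months, 5 to 10% withdrawn in months 0 to 6, hazard 2 to 3 times higher afterwards), 12-month OS is overstated by about 1 to 3 points; it is not biased if withdrawal is unrelated to prognosis. For the non-progressed group even the direction is unknown. The point does not extend to PFS, and no primary endpoint, error rate or dose decision is affected. It is worth correcting because the schedule contains an explicit restriction, not just a missing detail, and lifting it is cheap.

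**What to change.** - **Table 1-1, footnotes b and y:** collect survival status for all treated patients every 12 weeks until death, loss to follow-up or refusal of that contact, whatever their progression status, new therapy or investigator withdrawal.
- **Section 7.2:** distinguish stopping study drug, stopping visits, and refusing vital-status contact. State that investigator withdrawal does not by itself end vital-status collection.
- **Reconcile** the synopsis, Sections 4.1, 4.4, 7.1.1 and 7.2, and footnotes b and y, so that they give one rule.
- **Section 8.1.9 or the SAP:** say how a patient whose vital status is unknown after withdrawal is censored. Report the number of such patients, with a sensitivity analysis such as the best-case and worst-case bound above.

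The cost is an amendment to the wording and a few extra phone contacts, which Section 4.1 already implies. No extra visits, scans or samples are needed. Patients who refuse vital-status contact would still be censored.

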7.3 Loss of Participants to Follow-Up

A patient will be considered lost to follow-up if he or she repeatedly fails to return for scheduled visits and is unable to be contacted by the study site.

The following actions must be taken if a patient fails to return to the clinic for a required study visit:

- The site must attempt to contact the patient and reschedule the missed visit as soon as possible (and within the visit window, where one is defined) and counsel the patient on the importance of maintaining the assigned visit schedule and ascertain whether or not the patient wishes to and/or should continue in the study.
- In cases in which the patient is deemed lost to follow-up, the Investigator or designee must make every effort to regain contact with the patient (where possible, three telephone calls and, if necessary, a certified letter to the patient's last known mailing address or local equivalent methods). These contact attempts should be documented in the patient's medical record/eCRF.
- Should the patient continue to be unreachable, he/she will be considered to have withdrawn from the study.

8 Study Assessments and Procedures

Study procedures and their timing are summarized in the SoA (Table 1-1 [Parts 1 and 2]). Protocol waivers or exemptions are not allowed.

Immediate safety concerns should be discussed with the Sponsor immediately upon occurrence or awareness to determine if the patient should continue or discontinue study drug.

Adherence to the study design requirements, including those specified in the SoA, is essential and required for study conduct.

All screening evaluations must be completed and reviewed to confirm that potential patients meet all eligibility criteria. The Investigator will maintain a Screening Log to record details of all patients screened and to confirm eligibility or record reasons for screening failure, as applicable.

Procedures conducted as part of the patient's routine clinical management (e.g., blood count) and obtained before signing of the ICF may be utilized for Screening or baseline purposes provided the procedures met the protocol-specified criteria and were performed within the time frame defined in the SoA.

The maximum amount of blood collected from each patient over the duration of the study, including any extra assessments that may be required, will not exceed 500 mL.

Repeat or unscheduled samples may be taken for safety reasons.

